## 7.2.5 Dose-Limiting Toxicity (DLT)-Evaluable Population

The DLT-evaluable population will include patients who either experience a DLT during phase 1 or receive all scheduled doses and complete all study procedures in phase 1 without a DLT.

The DLT-evaluable population will be used for the analysis of DLTs.

## 7.3 Disposition of Subjects

Disposition of patients includes the number and percentage of patients for the following categories: patients in each of the study populations in Section 7.2, primary reason to discontinue from the treatment, patients discontinued from the study, and primary reason to discontinue from the study. All percentages will be based on the number of patients in the safety population.

A listing will be used to present data concerning the patient disposition.

## 7.4 Demographic and Other Baseline Characteristics

### 7.4.1 Demographics

Demographic and baseline characteristics will be summarized for patients in the safety population by dose level and disease type. Baseline demographic data to be evaluated will include sex, age, ethnicity, race, body weight, height, body surface area (BSA). The formulation for BSA is:

$$\text{BSA (m}^2\text{)} = \sqrt{\frac{\text{Ht(cm)} \times \text{Wt(kg)}}{3600}}$$

#### **7.4.2 Other Baseline Characteristics**

The following baseline characteristics will be summarized for patients in the safety population by dose level and disease type.

At initial diagnosis

- Months since initial diagnosis
- Disease Type
- Ann Arbor Stage
- Evidence of Bone Marrow Involvement
- Evidence of Extranodal Involvement

At Study Entry

- Evidence of Bone Marrow Involvement
- B Symptoms

#### **7.5 Medical History and Concurrent Medical Conditions**

General medical history of all patients will be presented in a by-patient listing in reported terms, ie, not coded.

B symptom assessments (fever, night sweats, and weight loss) and clinical evaluation of palpable liver and spleen will be presented over time in by-patient listings.

#### **7.6 Medication History and Concomitant Medications**

Medication history including prior antineoplastic therapy, prior surgery, prior radiation, and prior transplant procedure information will be presented in by-patient listings. The number and percentage of patients with any prior event will be tabulated by dose and by disease type.

Concomitant medications will be coded by preferred term using the World Health Organization (WHO) Drug Dictionary (March 2012 Version). Concomitant medication is defined as any medication administered between the first and the last days (inclusive) of the study. The number and percentage of patients taking concomitant medications from signing of informed consent form through 30 days after the last dose of brentuximab vedotin will be tabulated by Anatomical Therapeutic Chemical (ATC) classification pharmacological subgroup and WHO drug generic term.

Patients are counted once for each ATC pharmacological subgroup and once for each WHO preferred term.

Concomitant procedures will not be coded, but will be presented in a by-patient listing.

## 7.7 Study Drug Exposure and Compliance

The exposure to brentuximab vedotin will be characterized by total dose of drug received in mg, number of treated cycles, duration of treatment, and relative dose intensity (RDI, %).

$$\text{RDI (\%)} = 100\% * (\text{total dose administered (mg)} / \text{total dose expected (mg)})$$

Total dose expected is the summation of expected dose (dose level initially assigned multiply by weight) in each cycle during treatment.

A treated cycle is defined as a 21-day period, during which the patient receive any amount of brentuximab vedotin (scheduled for single dose in 21-day period). The duration of treatment is defined as time from the first study dose to 21 days after the last study dose:

$$\text{Duration of treatment} = \text{Last dose date} + 21 - \text{First dose date}$$

Action on study drug (including dose reduction) will be summarized by Cycle 1 through 16.

Dosing data including dose modification and action on drug will also be presented in a by-patient, by-cycle listing.

## 7.8 Efficacy Analysis

Response rates (OR, CR, PR), time to response, and duration of response will be conducted using the response-evaluable population. The other efficacy evaluations will be conducted using the safety population unless otherwise specified. All efficacy data will be summarized for the 7 groups listed in Section 7.1. If the sample size is too small to do a certain analysis in a group, no results will be presented for that group.

### 7.8.1 Primary Efficacy Endpoints

There is no primary efficacy endpoint in phase 1. The primary endpoint in phase 2 is overall response rate (ORR) of patients who achieve CR or PR as determined by an independent review facility (IRF) using PET, CT, MRI, and clinical assessment according to IWG revised response criteria.

The primary efficacy endpoint of ORR per IRF, along with CR rate, and PR rate will be summarized with 2-sided 95% exact confidence intervals. Response rates (OR, CR, and PR) will be summarized using the response-evaluable population.

### 7.8.2 Secondary Efficacy Endpoints

Besides response rates per IRF, response rates (ORR, CR, PR) per investigator assessments will also be summarized for all 7 groups listed in Section 7.1. Response rates will be summarized with 2-sided 95% exact confidence intervals.

The other secondary efficacy endpoints include time to progression (TTP), time to response, duration of response (DOR), event-free survival (EFS), progression-free survival (PFS), and overall survival (OS). TTP, DOR, EFS, and PFS will be estimated using independent review facility (IRF) assessment unless otherwise specified. Time to response and DOR will be

summarized using the response-evaluable population; TTP, EFS, PFS, and OS will be summarized using the safety population.

TTP is defined as the time from the first dose until the first subsequent documentation of objective tumor progression. TTP will be censored on the last radiological assessment of measured lesions documenting absence of PD for patients who do not have objective tumor progression.

Time to response is defined as the time from the first dose until the first documentation of objective tumor response (CR or PR). Time to response will be censored on the last radiological assessment of measured lesions documenting absence of CR or PR for patients who do not have a CR or PR.

Duration of response in subjects with response (CR or PR) is defined as the time from start of the first documentation of objective tumor response (CR or PR) to the first subsequent documentation of objective tumor progression or to death due to any cause, whichever comes first. Duration of response will be censored on the day following the date of the last radiological assessment of measured lesions documenting absence of PD for patients who do not have objective tumor progression and are still on study at the time of analysis, are given antitumor treatment other than the study treatment or stem cell transplant (SCT), or are removed from study prior to documentation of objective tumor progression.

EFS is defined as the time from the first dose until any cause of treatment failure: disease progression per IRF (including progression events during follow-up period), premature discontinuation of treatment for any reason (ie, not completing 16 cycles of treatment due to any reason), or death due to any cause, whichever occurs first. EFS will be censored on the last PFS assessment date if none of the above events occur during the study.

PFS is defined as the time from the first dose until disease progression or death due to any cause, whichever occurs first. PFS will be censored on the day following the date of the last radiological assessment of measured lesions documenting absence of PD for patients who do not have objective tumor progression and are still on study at the time of analysis, are given antitumor treatment other than the study treatment or SCT, or are removed from study prior to documentation of objective tumor progression. Patients lacking an evaluation of tumor response after their first dose will have their event time censored at the day of first dose.

OS is defined as the time from the first dose until death due to any cause. In the absence of confirmation of death, survival time will be censored at the last date the patient is known to be alive. Patients lacking data beyond the day of first dose will have their survival time censored at the day of first dose.

TTP, time to response, DOR, EFS, PFS, and OS will be analyzed using the Kaplan-Meier method, the 25th, 50th (median), and 75th percentiles, if estimable, will be presented along with the associated 2-sided 95% confidence intervals. The results will also be presented in figures (Kaplan-Meier plots).

A waterfall plot may be used to compare PFS per investigator from the current study versus PFS achieved with the last therapy received prior to study entry.

A waterfall plot will be used to summarize the greatest percent reduction in target lesions for individual patients.

Efficacy data will also be listed by patient.

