Overall response will be evaluated beginning after 2 cycles of therapy. Objective response over the course of the study will be assessed by an IRF according to the IWG Revised Response Criteria for Malignant Lymphoma [1]. Patients, including those who achieve a CR, a PR, or stable disease (SD), may receive brentuximab vedotin for up to 16 cycles. Treatment with brentuximab vedotin beyond 16 cycles may be permitted at the joint discretion of the sponsor and the investigator for those patients experiencing continued clinical benefit. Following administration of the final dose of brentuximab vedotin, patients will be monitored for adverse events for a minimum of 30 days. Patients will be followed for PFS and OS every 12 weeks for 12 months after the EOT visit. Thereafter, assessment for OS will continue every 6 months until the sooner of death or study closure or a maximum of 2 years after enrollment of the last patient. Patients who remain on treatment after Cycle 16 will be followed according to the above schedule or until study closure.

Study drug will be discontinued due to occurrence of unacceptable AE, progressive disease, patient withdrawal, or study termination. Patients may discontinue therapy at any time. Additionally, those patients who experience a CR and are candidates for hematopoietic stem cell transplantation must discontinue brentuximab vedotin prior to chemotherapy and transplant; these patients will be followed for survival analyses until study closure.

AEs will be assessed, and laboratory values, vital signs, and electrocardiograms (ECGs) will be obtained to evaluate the safety and tolerability of brentuximab vedotin.

Serial blood samples for determination of the concentration of brentuximab vedotin, total therapeutic antibody, and MMAE will be obtained during Cycle 1 and subsequent cycles at prespecified time points as described in the Schedule of Events (SOE) in the protocol.

Radiological evaluations, (CT scan or magnetic resonance imaging [MRI], and PET as clinically indicated), will be employed to assess the status of the patient's underlying disease. An evaluation of disease response will be assessed by an IRF according to the IWG Revised Response Criteria for Malignant Lymphoma [1] evaluated at Cycles 2, 4, 7, 10, 13, and 16 and

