then at the end of treatment. The scan frequency for patients who receive treatment past Cycle 16 is outlined in the Schedule of Events. Additional evaluations may be necessary when clinically indicated.

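### PFS, TTP and DOR are estimated on IRF assessment only, and no planned analysis would show the effect of progressions that the IRF does not confirm

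*SAP*

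**What the plan says.** **Reader.** SAP Section 7.8.2: "TTP, DOR, EFS, and PFS will be estimated using independent review facility (IRF) assessment unless otherwise specified". No other reader is then specified for the Kaplan-Meier estimates of PFS, TTP or DOR.

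**Stopping treatment.** SAP Section 4.4: "Study drug will be discontinued due to occurrence of unacceptable AE, progressive disease, patient withdrawal, or study termination". The text does not say whether the site or the IRF makes the progression call.

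**Censoring (Section 7.8.2).** For DOR and PFS, patients without objective progression who receive other antitumor treatment or come off study are censored the day after the last scan showing no PD. For TTP, patients without objective progression are censored at the last such scan; that rule has no clause on other treatment. Death from any cause is an event for DOR and PFS.

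**EFS (Section 7.8.2).** Events are death, any stop before 16 cycles, and "disease progression per IRF (including progression events during follow-up period)".

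**Investigator assessment (Section 7.8.2).** ORR, CR and PR are also summarized per investigator for all seven groups. For PFS there is only this: "A waterfall plot may be used to compare PFS per investigator from the current study", and the comparator in that plot is PFS on the last prior therapy.

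**IRF schedule (Section 4.4).** "An evaluation of disease response will be assessed by an IRF", "evaluated at Cycles 2, 4, 7, 10, 13, and 16" and "then at the end of treatment". The section adds: "Additional evaluations may be necessary when clinically indicated". PFS follow-up then continues 12-weekly for a year after EOT, with no reader named.

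**The concern.** In a single-arm trial with ORR as the phase 2 primary endpoint, DOR and PFS are the evidence on durability. Suppose treatment is stopped for progression and the IRF does not confirm it. The patient may then move to other therapy or leave the study, and is censored for PFS and DOR at about the time of suspected failure. TTP is censored at the last PD-free scan. Kaplan-Meier estimation assumes that such a patient has the same outlook as those still at risk. If the patient really was progressing, that is false and the curve sits too high.

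The SAP accepts that the reader matters for response, since it reports response rates both ways. It does not do so for the three endpoints where disagreement between readers changes events into censorings. A reader of the report would have no planned estimate from which to judge how much the durability figures depend on the choice of reader.

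**Working it through.** **1. The plan's own figure.** The SAP gives no figure for PFS, TTP, DOR or reader discordance. Its one checkable figure, in Section 6.0, is the exact 95% interval for 10 responses in 15. The Clopper-Pearson limits are 38.4% and 88.2%, which agree with the stated 38% and 88%.

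**2. One patient traced through Section 7.8.2.** Treatment stops before Cycle 16 for a progression that the IRF reads as no PD; other therapy follows.
- PFS and DOR: censored the day after the last scan that the IRF reads as PD-free.
- TTP: censored at the last PD-free scan.
- EFS: an event, because treatment stopped early.

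**3. Size under exponential times.** Let the true progression hazard be λ, with median ln 2/λ. Let a share q of true progressions be recorded as censored when they occur. The recorded event hazard is (1−q)λ, so Kaplan-Meier estimates exp(−(1−q)λt) and the median becomes ln 2/((1−q)λ), the true median times 1/(1−q).
- q = 10%: 1/0.9 = 1.11
- q = 20%: 1/0.8 = 1.25
- q = 30%: 1/0.7 = 1.43

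For an assumed true median of 6 months these give 6.7, 7.5 and 8.6 months. Which progressions go unconfirmed is random here, but each is censored at its own failure time, so the censoring is informative.

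**4. The same on a scan calendar.** A simulation of 100,000 patients used scans at weeks 6, 12, 21, 30, 39 and 48 (Cycles 2, 4, 7, 10, 13 and 16 at three weeks each), at EOT, and every 12 weeks for 48 weeks afterwards. The following are assumed and not in the SAP: true medians of 20, 35 or 52 weeks; independent stopping for reasons other than PD with a median of 40 weeks; no deaths; the values of q. PFS at 52 weeks, with follow-up scans read:

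| True median | q = 0 | q = 10% | q = 20% | q = 30% |
|---|---|---|---|---|
| 20 weeks | 0.196 | 0.233 | 0.276 | 0.326 |
| 35 weeks | 0.396 | 0.436 | 0.478 | 0.526 |
| 52 weeks | 0.535 | 0.571 | 0.607 | 0.646 |

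**5. If the IRF stopped reading at EOT (q = 0).**

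| True median | 52-week PFS, follow-up read | 52-week PFS, reads end at EOT | Patients with an event, read / not read |
|---|---|---|---|
| 20 weeks | 0.196 | 0.167 | 93% / 61% |
| 35 weeks | 0.396 | 0.363 | 79% / 44% |
| 52 weeks | 0.535 | 0.507 | 65% / 33% |

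At a true median of 52 weeks the median is no longer estimable. Events and estimability are lost, but PFS is not lengthened.

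**6. Scale in this trial.** With the SAP's example of 10 responders in an arm of 15, DOR rests on 10 patients. If all progressed, q = 20% would recode 10 × 0.2 = 2 events.

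**The case against.** Central review is a defensible prespecified choice and matches the primary endpoint. PFS, TTP and DOR are secondary and descriptive, with no hypothesis test, and the primary ORR is untouched. The plan also has partial safeguards: EFS, OS, response rates per investigator and by-patient efficacy listings. The 1/(1−q) factor assumes that every unconfirmed call is a true progression that is never confirmed later, that deaths add no events, and that the IRF never dates progression before the site does. The SAP supplies neither q nor a median.

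All of this is fair. It limits the weight of the point and makes the figures illustrations. It does not supply the missing comparison. OS and EFS measure something else, listings are not estimates, and the optional investigator PFS plot looks at prior therapy and not at the IRF.

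A reader might also infer three stronger things that the SAP does not support.
- *That every progression endpoint is affected.* EFS counts any stop before 16 cycles, so it captures most of these patients.
- *That progression is called at the site.* This is plausible, but Section 4.4 names no assessor.
- *That progressions after EOT are censored by rule and lengthen PFS further.* The listed IRF schedule does end at EOT. However, Section 4.4 elsewhere gives the IRF objective response throughout the study, PFS follow-up continues for a year, and the EFS definition counts IRF progression in follow-up. This is an unclear point and not a stated rule, and step 5 shows no upward bias from it when stopping is non-informative.

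**Conclusion.** The point holds for PFS, TTP and DOR. IRF assessment is the only planned basis for their Kaplan-Meier estimates. The censoring rules turn an unconfirmed true progression into an informative censoring, and no investigator-based estimate or discordance summary is planned that would reveal it. The direction is towards longer estimates. Under exponential times the median is inflated by 11%, 25% or 43% for q = 10%, 20% or 30%. The actual size is unknown because the SAP gives no discordance rate.

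Who reads scans after EOT is a separate clarification. What is at stake there is events and estimability; an upward bias is not shown.

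**What to change.** In SAP Section 7.8.2, keep the IRF analysis as the main one and add:

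1. Kaplan-Meier sensitivity analyses of PFS, DOR and TTP per investigator assessment, for the same groups as the main analysis, counting progressions in the 12-month follow-up.
2. A cross-table of IRF against investigator progression, by status and date.

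As a clarification only, reconcile the IRF schedule in Section 4.4, which lists no evaluation after EOT, with the EFS definition's IRF progression during follow-up. Apply the same rule to PFS, TTP and DOR.

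**Cost.** SAP wording and a rerun of existing programs. The sensitivity analyses need no new reads, because investigator assessments are already used for response rates and foreseen for the optional PFS plot. The downside is a few more tables and possibly a shorter investigator-based estimate beside the IRF one.

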## 7.0 METHODS OF ANALYSIS AND PRESENTATION

### 7.1 General Principles

In general, descriptive statistics (number of observations, mean, standard deviation (StdDev), median, minimum, and maximum) will be used to summarize continuous variables. Frequencies and percentages will be used to summarize categorical variables. Time-to-event data will be analyzed using the Kaplan-Meier method and results will be summarized by the 25th, 50th (median), and 75th percentiles, if estimable, with associated 2-sided 95% confidence intervals, as well as the percentage of censored observations.

Unless otherwise specified, safety and efficacy data will be summarized in the following 7 groups: 1.4 mg/kg phase 1 only; 1.8 mg/kg phase 1 only; 1.8 mg/kg phase 1&2 HL only; 1.8 mg/kg phase 1&2 sALCL only; 1.8 mg/kg phase 1&2 sALCL in first relapse only; 1.8 mg/kg all patients; all patients. Pharmacokinetic analyses will be summarized by dose and treatment cycle.

The baseline value is defined as the value collected at the time closest to, but prior to, the start of study drug administration, unless otherwise specified. A windowing convention will be used to determine the analysis value for a given study visit for observed data analyses.

All available efficacy and safety data will be included in data listings and tabulations. Data that are potentially spurious or erroneous will be examined under the auspices of standard data management operating procedures. In general, there will be no imputation of missing data. For time-related endpoints, subjects who have no specified events will be censored as specified for each respective endpoint in Section 7.8. Imputation rules for missing dates of AEs and concomitant medications are detailed in Sections 7.1.3 and 7.1.4.

SAS Version 9.2 (or higher) will be used for all analyses.

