## 7.2.4 Response-Evaluable Population

The response-evaluable population will include patients who receive at least 1 dose of study drug, have measurable disease at baseline, and have 1 postbaseline disease assessment.

The response-evaluable population will be used for analyses of disease response, time to response and duration of response.

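### Kaplan-Meier time to response censors patients who progress or die without responding, so its upper percentiles, and the median when ORR is below 50%, can contradict the ORR

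*SAP*

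**What the plan says.** SAP section 7.8.2 measures time to response from first dose to the first documented CR or PR. For patients with neither, it states: "Time to response will be censored on the last radiological assessment of measured lesions documenting absence of CR or PR". Progression and death without response are not distinguished from ongoing follow-up.

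The estimator is fixed later in the same section: "TTP, time to response, DOR, EFS, PFS, and OS will be analyzed using the Kaplan-Meier method". The 25th, 50th and 75th percentiles, where estimable, are to be given with 95% confidence intervals and plots. Section 7.1 sets the same general rule ("Time-to-event data will be analyzed using the Kaplan-Meier method") and adds the percentage censored.

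Non-responders are in the risk set, because section 7.2.4 says: "The response-evaluable population will be used for analyses of disease response, time to response and duration of response". The primary ORR (section 7.8.1) uses the same population, as a simple proportion with an exact 95% interval.

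On what happens at progression, section 4.4 states: "Study drug will be discontinued due to occurrence of unacceptable AE, progressive disease, patient withdrawal, or study termination".

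**The concern.** Kaplan-Meier is valid when a censored patient has the same future chance of the event as the patients still at risk. A patient who has died cannot respond. A patient who has progressed is taken off study drug and is not comparable with one still on treatment and able to respond. The plan nevertheless passes the unused probability of these patients on to those who remain. One minus the Kaplan-Meier estimate then exceeds the proportion responding whenever a response comes after such a censoring.

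The result would be an internally inconsistent report. In the same population and groups as the ORR, the tables could show a finite 75th percentile when fewer than 75% of patients responded, or a finite median when fewer than half did, with a plot rising above the ORR. Time to response is a named secondary endpoint in both phases.

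Patients who stop drug without progressing are a weaker case, because their PFS follow-up continues, and they are not part of this point.

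**Working it through.** **The plan's own figure.** Section 6.0 gives 10/15 = 66.7% with an exact 95% interval of (38%, 88%). The Clopper-Pearson calculation gives (38.4%, 88.2%), which agrees.

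**Inputs from the SAP.** n = 15 per disease group (6.0); 21-day cycles and scans at Cycles 2, 4, 7, 10, 13 and 16 (4.4); at least one postbaseline assessment for entry to the population (7.2.4); the censoring rule and estimator quoted above (7.8.2).

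**Assumptions.** Scans fall at the end of Cycles 2, 4 and 7: 2 × 21 = day 42, 4 × 21 = day 84, 7 × 21 = day 147. The split of responses and censorings over scans is illustrative. Every censored patient has progressed or died without response. At a tied scan, responses are counted before censorings.

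**Formulas.** Kaplan-Meier: S(t) = product of (1 − responses/at risk), and the planned curve is 1 − S(t). Cumulative incidence, with every non-responder progressed or dead: responses to date / 15.

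**Case 1, ORR 10/15.** Responses 7, 2, 1 at days 42, 84, 147; censored 3 at day 42 and 2 at day 84.
- Day 42: S = 8/15 = 0.533
- Day 84 (5 at risk): 0.533 × 3/5 = 0.320
- Day 147 (1 at risk): 0.320 × 0/1 = 0

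**Case 2, ORR 7/15.** Responses 5, 2 at days 42, 84; censored 4, 3, 1 at days 42, 84, 147.
- Day 42: S = 10/15 = 0.667
- Day 84 (6 at risk): 0.667 × 4/6 = 0.444

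**Case 3, ORR 5/15.** Responses 3, 1, 1 at days 42, 84, 147; censored 6, 3, 1.
- Day 42: S = 12/15 = 0.800
- Day 84 (6 at risk): 0.800 × 5/6 = 0.667
- Day 147 (2 at risk): 0.667 × 1/2 = 0.333

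| Case | 1 − KM at d42, d84, d147 | Cumulative incidence | Percentile in conflict |
|---|---|---|---|
| 10/15 | 46.7%, 68.0%, 100% | 46.7%, 60.0%, 66.7% | 75th: d147 against not reached |
| 7/15 | 33.3%, 55.6%, 55.6% | 33.3%, 46.7%, 46.7% | median: d84 against not reached |
| 5/15 | 20.0%, 33.3%, 66.7% | 20.0%, 26.7%, 33.3% | median: d147 against not reached |

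In case 1 the 25th percentile (d42) and the median (d84) are the same under both methods.

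**Milder patterns and limits, all at 10/15.**
- Responses 8 at day 42 and 2 at day 84; censored 3, 1, 1 at days 42, 84, 147: S = 7/15 × 2/4 = 0.233. The curve reaches 76.7% and the 75th percentile is day 84.
- Responses 9 and 1, same censoring: S = 6/15 × 2/3 = 0.267. The curve reaches 73.3%, above the ORR, but the 75th percentile remains not estimable.
- All 10 responses at day 42: S = 5/15 = 0.333. The curve ends at 66.7%, equal to the ORR.
- Non-responders censored only at or after the last response: the curve again ends at 66.7%.

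**The case against.** The rule is complete and consistent: event, censoring, estimator and population are all specified. The SAP never says the Kaplan-Meier curve estimates the proportion responding; the ORR has its own analysis. Time to response is descriptive, with no test or decision attached. At the SAP's own 66.7% example only the 75th percentile and the tail of the plot are at risk, and the median is contradicted only if the ORR is below 50%. The illustrations assume the timing and take every non-responder as progressed or dead; in case 1 the curve reaches 100% only because the last patient at risk responds. The percentage censored, the patient listings and the ORR would let a careful reader see the discrepancy.

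Most of this stands as a limit on size. The effect depends on response timing, which the document does not predict, and it does not touch the primary analysis. It does not rescue the method. The percentage censored reveals non-response but corrects neither the percentiles nor the plot. Reporting percentiles only if estimable is no safeguard either, because the distortion is what makes a percentile appear estimable. A percentile of time to response over all evaluable patients will be read as the time by which that share had responded, and the plan can produce one that was never reached.

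**Conclusion.** The concern holds. Followed exactly, the plan can report a time-to-response percentile that the observed proportion responding never attains. The condition is that at least one response comes after a patient who progressed or died without response has been censored. At an ORR near 66.7% the exposure is the 75th percentile and the upper part of the curve; below 50% it extends to the median. With all responses at the first scan, or with such censoring only at or after the last response, there is no distortion. The sizes shown rest on assumed scan-by-scan timing in 15 patients and on all non-responders having progressed or died. The matter is confined to one descriptive secondary endpoint and should be corrected; the ORR and its exact interval stand.

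**What to change.** 1. In section 7.8.2, take time to response out of the list of endpoints analysed by Kaplan-Meier, and note the exception beside the general time-to-event sentence in section 7.1.
2. Summarise time to response as median and range among responders, labelled as conditional on response.
3. If a curve over all response-evaluable patients is wanted, use the Aalen-Johansen cumulative incidence of response with progression or death without response as competing events. Align the censoring sentence in section 7.8.2 so that only patients without response, progression or death are censored at their last assessment. This curve ends at the ORR when every non-responder has progressed or died; with other censoring it need not match exactly.

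A simpler variant that keeps the Kaplan-Meier machinery is to censor progressors and deaths without response beyond the longest follow-up, so that they stay in the risk set. In the cases above this gives the same curve as cumulative incidence.

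The cost is SAP wording and minor programming, with no new data. The drawback of the responders-only summary is that it says nothing about non-responders, so it must be read beside the ORR.
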